6. GENERAL STATISTICAL CONSIDERATIONS

6.1. General Principles

Tabulations will be used extensively to summarize the data. All continuous variables will be summarized using the following descriptive statistics: n (sample size), mean, standard deviation, median, maximum and minimum. The frequency and percentages (based on the sample size) of observed levels will be reported for all categorical measures. Wilson confidence intervals for binomial proportions and difference in binomial proportions will be computed for efficacy variables. For the hypothesis tests comparing treatment groups with respect to efficacy outcomes, the two-sided Pearson Chi-Square test will be used. A 5% two-sided significance level will be used; i.e. two-sided 95% confidence intervals will be generated.

All summary tables will be structured with a column/sub-table for each treatment group (Azithromycin, Doxycycline, and All Subjects). In general, all data will be summarized by treatment group and/or site, and when appropriate by visit number. The total population size relevant to that table/column if applicable, including any missing observations will be displayed in the tables.

Data listings will be provided for all data. Note that in the data listings, Subject ID is the unique subject identifier, not the Study ID used on study and dates will not be included, only Study Day.

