6.8. Multiple Comparisons/Multiplicity

O'Brien-Fleming boundaries will be utilized for the interim and final analyses to account for the formal interim analysis while maintaining an overall Type I error rate of 5%. Section 8 for details.

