8.2. Final Analysis

8.2.1. Primary Efficacy Analysis

The primary efficacy endpoint for the final analysis is the proportion of subjects with microbiologic cure in each study arm at Day 29. See Section 3.3.1 for the definition of microbiologic cure.

A test of hypothesis comparing the proportion of subject with microbiologic cure at Visit 3 (Day 29), will be conducted in the CC population. The null hypothesis for the comparison is that there is no difference in proportions between treatment arms, with a two-sided alternative that considers the possibility of a difference in either direction. The test will be conducted using a Pearson Chi-Square test at the 5% two-sided significance level. The number of subjects, the proportion of subjects with microbiologic cure, and the 95% Wilson confidence interval for the proportion of subjects with microbiologic cure will be presented overall and by treatment group. In addition, the difference in proportions between the Azithromycin group and the Doxycycline group and 95% Wilson confidence intervals will be presented.

The test statistic will be compared to the O'Brien Fleming bound calculated in the study's sample size calculations to determine significance. At the final analysis the bound is |1.97743|, thus if the test statistic is either greater than 1.97743 (doxycycline cure rate is higher than azithromycin cure rate) or less than -1.97743 (azithromycin cure rate is higher than doxycycline cure rate), then the resulting interpretation is that the cure rates are significantly different between arms. Otherwise, the resulting interpretation is that the cure rates are not significantly different between arms.

The above analyses, apart from the O'Brien Fleming bound comparisons will be repeated in the ITT and PP analysis populations.

See [Table 13](#), [Table 14](#), and [Table 15](#). See Section 6.1 for pseudocode to fit the above analyses. Individual efficacy response data is presented in [Listing 6](#).

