13. REPORTING CONVENTIONS

P-values ≥ 0.001 and ≤ 0.999 will be reported to three decimal places; p-values less than 0.001 will be reported as “ <0.001 ”; p-values greater than 0.999 will be reported as “ >0.999 ”. The mean, median, standard deviation, and any other statistics other than quantiles, will be reported to one decimal place greater than the original data. Quantiles other than the median will use the same number of decimal places as the original data. Proportions will be presented to two decimal places; values <0.01 will be presented as “ <0.01 ”. Percentages will be reported to the nearest whole number; values $< 1\%$ will be presented as “ <1 ”. Estimated parameters, not on the same scale as raw observations (e.g. regression coefficients) will be reported to three significant figures.

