Eligible for CC Analysis Population		x	x	x	x	x	x
Excluded from CC Analysis Population	Any Reason	x	x	x	x	x	x
	Reason 1	x	x	x	x	x	x
	Reason 2	x	x	x	x	x	x
	...	x	x	x	x	x	x

Notes: Denominator for percentages is the number of subjects enrolled (N) in the study randomized to the specified treatment group.

Subjects will be counted for a particular reason for exclusion if they met the criterion. As subjects may meet more than one criterion, the sum of the individual reasons may add up to more than the subjects excluded.

Table 12: Interim Analysis Microbiological Cure Rates – CC Population

Treatment Group	Number of Subjects	Number of Subjects with Microbiologic Cure	Interim Microbiologic Cure Proportion	Interim Confidence Interval	Test Statistic	Critical Value
Group A	x	x	0.xx	0.xx, 0.xx	x.x	+/- 2.79651
Group B	x	x	0.xx	0.xx, 0.xx		

Implementation Notes:

Depending on the observed test statistic value, the last two columns will be rounded accordingly. The appropriate critical value (positive vs. negative) will be displayed according to the sign of the test statistic.

Table 13: Microbiologic Cure at Visit 3 (Day 29) by Treatment Group - CC Population

Treatment Group	Number of Subjects with Microbiologic Cure n	Number of Subjects N	Proportion of Subjects with Microbiologic Cure	Proportion of Subjects with Microbiologic Cure 95% CI	Difference in Proportion of Subjects with Microbiologic Cure between Doxycycline and Azithromycin	Difference in Proportion of Subjects with Microbiologic Cure between Doxycycline and Azithromycin 95% CI	Test Statistic	Critical Value	P-Value ^a
Doxycycline	x	x	0.xx	0.xx, 0.xx	0.xx	0.xx, 0.xx	x.x	+/- 1.97743	0.xxx
Azithromycin	x	x	0.xx	0.xx, 0.xx					
All Subjects	x	x	0.xx	0.xx, 0.xx					

Note: The denominator for proportions is based on the number of subjects enrolled in the respective treatment group.

^a P-value from the two-sided Pearson Chi-Square test.

Implementation Notes:

Depending on the observed test statistic value, the last two columns will be rounded accordingly. The appropriate critical value (positive vs. negative) will be displayed according to the sign of the test statistic.

Tables with similar format:

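### Does the rounding note under the SAP Table 13 shell hide whether the final test statistic crosses 1.97743?

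*SAP*

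**What the plan says.** SAP 8.2.1 runs a Pearson chi-square test in the complete case population and uses the O'Brien-Fleming bound from the "sample size calculations to determine significance". The arms differ significantly "if the test statistic is either greater than 1.97743 (doxycycline cure rate is higher than azithromycin cure rate) or less than -1.97743", the negative side standing for a higher azithromycin cure rate. SAP 6.8 says the boundaries serve the purpose of "maintaining an overall Type I error rate of 5" percent.

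The Table 12 shell (interim) ends with two columns, Test Statistic and Critical Value. The Table 13 shell (final) ends with three: Test Statistic (placeholder x.x), Critical Value (+/- 1.97743) and P-Value. The same implementation note stands under both: "Depending on the observed test statistic value, the last two columns will be rounded accordingly". The Table 13 p-value footnote reads "P-value from the two-sided Pearson Chi-Square test" and gives no threshold.

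On format, SAP 13 says of p-values between 0.001 and 0.999 that they "will be reported to three decimal places", and also that "Proportions will be presented to two decimal places". SAP 6.1 adds "A 5% two-sided significance level will be used; i.e. two-sided 95% confidence intervals will be generated". The interval for the difference is the Newcombe interval (SAP 6.1.1).

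**The concern.** In Table 12 the note covers the statistic and its bound, which is what one wants. In Table 13 the same words point to the bound and the p-value. That leaves the deciding statistic at one decimal beside a bound given to five, and it clashes with the fixed three decimals for p-values.

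One decimal cannot resolve a bound at 1.97743, and the neighbouring columns do not announce the answer. The nominal p-value that matches the bound is written nowhere, while the text speaks of a 5% two-sided level. The 95% interval is not adjusted for the interim look, does not invert the Pearson test, and is not labelled descriptive.

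Table 13 reports the trial's only formal hypothesis test (protocol 10.1). In a close result, a reader who compared the printed p-value with 0.05 could call a difference significant when SAP 8.2.1 says it is not.

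**Working it through.** **1. The bounds.** Inputs: overall alpha 0.05 (SAP 6.8), one interim look at 123 of 246 (SAP 5), so the correlation between the two z-statistics is sqrt(0.5). Solving P(|Z1| > C·sqrt(2) or |Z2| > C) = 0.05 with the bivariate normal gives C = 1.97743 and C·sqrt(2) = 2.79651. Both SAP bounds are reproduced, and overall alpha at these bounds is 0.0500.

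**2. The matching p-value.** 2·(1 − Φ(1.97743)) = 0.0480. If the final test were instead judged at p < 0.05 (|z| > 1.96), overall alpha would be 0.0520. That is not the SAP's rule.

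**3. What one decimal does.** With 123 per arm and x1, x2 cures, p̄ = (x1 + x2)/246 and z = [(x1 − x2)/123] / sqrt(p̄(1 − p̄)·2/123), the signed root of the uncorrected Pearson chi-square.

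- 116 v 107: p̄ = 223/246 = 0.9065, difference 9/123 = 0.0732, standard error 0.0371, z = 1.971, p = 0.0487. Below the bound.
- 120 v 113: p̄ = 233/246 = 0.9472, difference 7/123 = 0.0569, standard error 0.0285, z = 1.995, p = 0.0461. Above the bound.

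Both statistics print as 2.0.

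**4. What the rest of the row shows for these two results.**

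| Printed item | 116 v 107 | 120 v 113 |
|---|---|---|
| Cures / subjects | 116/123, 107/123 | 120/123, 113/123 |
| Proportions | 0.94, 0.87 | 0.98, 0.92 |
| Difference | 0.07 | 0.06 |
| Newcombe 95% CI before rounding | −0.0008 to 0.1497 | −0.0010 to 0.1209 |
| p-value | 0.049 | 0.046 |
| SAP 8.2.1 conclusion | not significant | significant |

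The lower confidence limits both round to zero, but the counts, proportions, difference, upper limit and p-value all differ. The counts alone give z to any precision.

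**5. Every such case at 123 per arm.** With 80 to 123 cures in each arm, 19 unordered pairs of counts print 2.0.

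- 13 cross the bound. Their largest p-value is 0.0479 (95 v 81), so all print 0.048 or lower.
- 6 do not. Four print 0.050 (94 v 80, 106 v 94, 110 v 99, 118 v 110) and two print 0.049 (101 v 88, 116 v 107).

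At these arm sizes the three-decimal p-value separates the two groups completely.

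**6. How often it could arise.** Exact binomial probabilities, 123 per arm, ignoring an interim stop:

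| Cure rates | Prints 2.0 | Prints 2.0, bound not crossed | Bound not crossed but p < 0.05 |
|---|---|---|---|
| 87% v 87% | 0.9% | 0.3% | 0.3% |
| 95% v 85% | 2.8% | 1.9% | 1.3% |
| 96% v 86% | 2.7% | 2.1% | 1.0% |
| 97% v 87% | 2.4% | 1.7% | 0.5% |
| 98% v 88% | 1.8% | 0.7% | 0.1% |
| 99% v 89% | 0.8% | 0.1% | 0.0% |

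The last column is the relevant one, because nobody would read p above 0.05 as significant.

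**The case for a change.** The strongest case for a change is that the primary result table should show its own conclusion without a hand calculation. The note shows that the authors wanted the display to adapt to the observed statistic, and its literal wording misses the column that matters. The three-decimal p-value is not a complete safeguard either. Once arm sizes drift from 123 each, a printed 0.048 covers z from 1.973 to 1.982. For example, 118/123 v 109/122 gives z = 1.97696, which misses the bound, and 121/123 v 112/120 gives z = 1.97768, which crosses it; both print p = 0.048. The confidence interval does not help: 120 v 113 and 123 v 119, each of 123, cross the bound while their Newcombe intervals include zero. The SAS code in SAP 6.1.1 also returns an unsigned chi-square, whereas SAP 8.2.1 needs a signed statistic.

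The mislabelled columns and the ambiguity of a printed 0.048 stand. They concern display only. The note opens by referring to the observed test statistic, and its next sentence deals with the sign of the critical value, so a programmer will take it to mean those two columns, as in Table 12. A chi-square cannot fall below −1.97743, and SAP 8.2.1 says which arm each sign favours, so the signed root is the only workable reading. Writing the bound as p < 0.0480 would restate the same rule on another scale. The SAP does not make the interval a decision criterion, and a Newcombe interval need not agree with a Pearson test even without an interim look.

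**Conclusion.** This is a clerical slip in a table mock-up, and the plan needs no change. The bounds are right, overall type I error is 0.0500, and SAP 8.2.1 assigns the decision to the bound, applied to the unrounded statistic. An alpha of 0.0520 would require a reader to set aside both that section and the critical value printed in the same row.

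The exposure is a reading risk near the bound: 0.3% under equal 87% cure rates and 0.0% to 1.3% across the SAP Table 3 scenarios. Even then, the printed counts settle the matter. These figures assume 123 analysed per arm and no interim stop. Other arm sizes can make a printed 0.048 ambiguous, but the counts still resolve it. Naming the two columns in the note would be a harmless tidy-up if the shells are reissued; no result or conclusion depends on it.

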Eligible subjects who consent to participate will be enrolled in the trial, which involves three scheduled visits over a 29-day period (Screening/Enrollment on Day 1, Follow-up Visits on Days 15 and 29). At Visit 1, after subjects provide informed consent and are determined to be eligible, study staff will collect baseline information on the subject's current rectal symptoms, sexual, STD and HIV history, and clinical and laboratory findings. Subjects will provide one baseline rectal swab for CT and LGV testing (NAAT) (clinician- or self-collected, to be obtained according to local clinic standard operating procedures (SOPs)). Subjects who consent to collection and storage of swabs for future use will have two additional swabs collected by the clinician (one for storage in culture media and one frozen). All subjects will be counseled on study drug side effects, randomized (1:1) to receive azithromycin and placebo doxycycline (Arm 1) or doxycycline and placebo azithromycin (Arm 2), and administered the full dose of azithromycin (or placebo) plus one dose of doxycycline (or placebo) in the clinic. Research staff will attempt to recruit the partners of enrolled subjects for screening visits by offering enrolled subjects the option to deliver information cards to their partners.

At Visit 1, subjects will be informed of the option to self-collect Visit 2 and/or Visit 3 swabs outside of the clinic, mail the specimens to the laboratory, and receive follow-up phone calls at

those time points rather than return to the clinic (hereafter referred to as the mail-in option). Subjects who opt for the mail-in option will receive supplies for specimen collection kit and instructions.

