6.2 Dosage, Preparation and Administration of Study Drugs

A site Research Pharmacist may be delegated the responsibility of study drug dispensation, must be a licensed registered pharmacist, and is the preferred healthcare practitioner to be delegated this activity. If a Research Pharmacist is not available, a physician, nurse practitioner, physician assistant, registered nurse, or other authorized healthcare practitioner who is a member of the clinical study staff may be delegated to dispense study drug. These personnel must be licensed, trained, and qualified to prepare investigational study drugs and must be authorized to dispense study drug under state and local rules and regulations.

Subjects will be randomized to one of two treatment assignments:

- Azithromycin 250 mg x 4 (1 gram) orally as a single dose plus placebo doxycycline x 1 orally twice daily for 7 days (14 capsules total)
- Doxycycline 100 mg x 1 orally twice daily for 7 days (14 capsules total) plus placebo azithromycin x 4 orally as a single dose

The study clinician or designee will obtain the study drug kit corresponding to the subject's randomized treatment assignment. Each kit will contain two vials of study drugs. Packaging is described in Section 6.1.2 and study design and study arms are described in Section 4.

Study staff will instruct all subjects to take four azithromycin 250 mg capsules (or placebo) as a single dose plus one doxycycline 100 mg capsule (or placebo) at the end of the enrollment visit

(Day 1), observing these doses before subjects leave the clinic. Study staff will provide instructions for continued twice-daily doxycycline (or placebo) for 7 days to complete 14 doses. Subjects will be asked to bring the vial of doxycycline (or placebo) back to the clinic at Visit 2.

A subject who vomits the first dose of azithromycin (or placebo) and one doxycycline capsule (or placebo) within 2 hours of ingestion will be asked to return to the study clinic within 48 hours of the initial dose for re-treatment. Refer to the MOP for re-treatment procedures. Subjects who vomit within 2 hours of re-treatment will be withdrawn from the trial and treated per routine standard of care.

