3.1.3. Exploratory Objective

To assess the effect of HIV status, adherence to study drug, antacid medication use and symptomatic status on microbiologic cure at Day 29.

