3.3.4. Treatment Adherence

Subjects will be considered sufficiently adherent with study treatment if they take the initial dose of azithromycin (or placebo) and initial dose of doxycycline (or placebo) and at least 9 additional doses of doxycycline (or placebo) within 10 days (inclusive) of the completed initial dose.

An alternative definition of sufficiently adherent will also be explored. Subjects will be considered sufficiently adherent under this alternate definition if they:

- take the initial dose of azithromycin (or placebo) and initial dose of doxycycline (or placebo), and
- take at least 80% of the scheduled doses of doxycycline capsule (or placebo) (i.e., at least 12 of the 14 doses) as assessed by the subject-reported number of missed doses within in 7 days (inclusive) of the completed initial dose.

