6.3.2.3. Per-Protocol (PP) Population

The Per-Protocol (PP) Population includes all randomized subjects who meet all inclusion/exclusion criteria at enrollment, have a positive baseline rectal CT NAAT result, have post-baseline microbiologic data available, sufficiently adhere to the assigned study drug regimen (defined in Section 3.3.4), and do not experience either of the following after enrollment and before a particular visit (Day 15 for analyses at Day 15, and Day 29 for analyses at Day 29):

- Receipt of an antibiotic active against CT
- Have condomless receptive anal sex

For analyses at Day 15, microbiologic data must be available from the Day 15 visit. Likewise, for analyses at Day 29, microbiologic data must be available from the Day 29 visit.

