8.2.3. Exploratory Efficacy Analyses

The exploratory outcome measure is the proportion of subjects with microbiologic cure in each study arm at Day 29 within separate subgroups defined by HIV status at baseline, adherence to study drug, antacid medication use, and symptomatic status (all defined in Section 3.3). For the HIV analyses, subjects who enrolled HIV negative but became HIV positive prior to their Day 29 visit will be included in the ITT analysis and excluded from CC and PP analyses.

The number of subjects, the proportion of subjects with microbiologic cure at Visit 3 (Day 29) will be summarized in each subgroup overall and by treatment. The point estimates for treatment-specific proportions and difference in proportions as well as corresponding 95% Wilson confidence intervals will be present within each subgroup at Visit 3 (Day 29) for each analysis population. Proposed summaries begin at [Table 25](#) and end at [Table 36](#).

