Table 28: Microbiologic Cure at Visit 3 (Day 29) by Treatment Group and Adherence to Treatment - CC Population

Table 29: Microbiologic Cure at Visit 3 (Day 29) by Treatment Group and Adherence to Treatment - ITT Population

Table 30: **Microbiologic Cure at Visit 3 (Day 29) by Treatment Group and Adherence to Treatment - PP Population**

Table 31: **Microbiologic Cure at Visit 3 (Day 29) by Treatment Group and Use of Antacids - CC Population**

Table 32: **Microbiologic Cure at Visit 3 (Day 29) by Treatment Group and Use of Antacids - ITT Population**

Table 33: **Microbiologic Cure at Visit 3 (Day 29) by Treatment Group and Use of Antacids - PP Population**

Table 34: **Microbiologic Cure at Visit 3 (Day 29) by Treatment Group and Baseline Symptomatic Status - CC Population**

Table 35: **Microbiologic Cure at Visit 3 (Day 29) by Treatment Group and Baseline Symptomatic Status - ITT Population**

Table 36: **Microbiologic Cure at Visit 3 (Day 29) by Treatment Group and Baseline Symptomatic Status - PP Population**

Implementation Notes:

For Tables 26 – 28, the subgroup labels will be “HIV Negative” and “HIV Positive”.

For Tables 29 – 31, four subgroups will be included in the summaries, two for the primary definition of adherence (with subgroup labels “Adherent – Primary Def’n” and “Not Adherent – Primary Def’n”) and two for the alternative definition of adherence (with subgroup labels “Adherent – Alternate Def’n” and “Not Adherent – Alternate Def’n”).

For Tables 32 – 34, the subgroup labels will be “No Antacid Use” and “Antacid Use”.

For Tables 35 – 37, the subgroup labels will be “Asymptomatic” and “Symptomatic”.

Table 37: Summary of Categorical Demographic and Baseline Characteristics by Site - All Enrolled Subjects

Variable	Characteristic	University of Washington (N=X)		Fenway Health (N=X)		All Subjects (N=X)	
		n	%	n	%	n	%
Ethnicity	Not Hispanic or Latino	x	x	x	x	x	x
	Hispanic or Latino	x	x	x	x	x	x
	Not Reported	x	x	x	x	x	x
	Unknown	x	x	x	x	x	x
Race	American Indian or Alaska Native	x	x	x	x	x	x
	Asian	x	x	x	x	x	x
	Native Hawaiian or Other Pacific Islander	x	x	x	x	x	x
	Black or African American	x	x	x	x	x	x
	White	x	x	x	x	x	x
	Multi-Racial	x	x	x	x	x	x
	Unknown	x	x	x	x	x	x
Rectal CT Symptomatic Status	Symptomatic	x	x	x	x	x	x
	Asymptomatic	x	x	x	x	x	x
Inguinal Lymphadenopathy	Yes	x	x	x	x	x	x
	No	x	x	x	x	x	x

Note: N=Number of subjects enrolled at the specified site.

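### The adherence tables (SAP Tables 28–30) plan no estimate of adherence to active drug, and their pooled rows dilute any doxycycline adherence association

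*SAP*

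**What the plan says.** The objective (SAP 3.1.3) is "To assess the effect of HIV status, adherence to study drug, antacid medication use and symptomatic status on microbiologic cure at Day 29".

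Under the primary definition in SAP 3.3.4, a subject is adherent if he takes both initial doses and "at least 9 additional doses of doxycycline (or placebo) within 10 days (inclusive) of the completed initial dose". The alternative definition asks for at least 12 of the 14 capsules within 7 days. Neither definition differs by arm.

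The regimens do differ. Protocol 6.2 gives one arm as "Azithromycin 250 mg x 4 (1 gram) orally as a single dose plus placebo doxycycline x 1 orally twice daily for 7 days", so all 14 twice-daily capsules in that arm are placebo. Protocol Section 4 says that at Visit 1 subjects are "administered the full dose of azithromycin (or placebo) plus one dose of doxycycline (or placebo) in the clinic". Active azithromycin is thus taken under observation, with a re-treatment provision after vomiting.

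For the analysis, SAP 8.2.3 says cure "will be summarized in each subgroup overall and by treatment", with treatment-specific proportions, the difference between treatments and Wilson intervals. The Appendix 1 implementation note adds that "four subgroups will be included in the summaries, two for the primary definition of adherence", and two for the alternative one. (The note is addressed to Tables 29–31; by title the adherence tables are 28–30.) These tables follow the Table 19 layout: within each stratum, a doxycycline row, an azithromycin row, an All Subjects row, and one doxycycline minus azithromycin difference.

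SAP 6.3.2.3 makes sufficient adherence under Section 3.3.4 a condition of the per-protocol (PP) population.

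**The concern.** An azithromycin man who keeps his observed dose down but takes too few placebo capsules is classed Not Adherent despite full exposure to active drug. In that arm the label mixes such men with any who never completed the active dose. In the doxycycline arm the same label means under-exposure to active drug.

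Two consequences follow. The All Subjects rows combine two different things under one label. And the between-arm difference in the Not Adherent stratum sets under-dosed doxycycline against mostly fully dosed azithromycin. It can reverse sign relative to the main result without saying anything about the effect of adherence. A reader looking for the answer to the stated objective would find only these pooled rows and between-arm differences, plus two doxycycline rows to subtract by eye.

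**Working it through.** The documents give no figure for the adherence analysis, so there is none to reproduce. The arithmetic below is illustrative.

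**Inputs from the documents.** 246 evaluable men randomized 1:1, so 123 per arm. Cure D = 95% for doxycycline and A = 85% for azithromycin (the conservative rates in SAP Section 5).

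**Assumptions.** D applies to adherent doxycycline men. Azithromycin cure is A whatever the placebo count. Cure in non-adherent doxycycline men is p = 80%, 70% or 60%. Non-adherence is 10% per arm, varied from 5% to 20%.

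**1. Doxycycline rows.** Adherent minus not adherent = D − p = 15, 25 or 35 points.

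**2. All Subjects rows.** Let a and b be doxycycline's share of the adherent and of the non-adherent men. The pooled contrast is

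[aD + (1 − a)A] − [bp + (1 − b)A] = b(D − p) + (a − b)(D − A).

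- Equal non-adherence: a = b = 0.5, giving 7.5, 12.5 or 17.5 points, exactly half.
- 20% doxycycline, 5% azithromycin: a = 0.80/1.75 = 0.457 and b = 0.20/0.25 = 0.80, giving 8.6, 16.6 or 24.6 points (57% to 70% of the association).
- 5% doxycycline, 20% azithromycin: a = 0.543 and b = 0.20, giving 6.4, 8.4 or 10.4 points (43% down to 30%).
- No adherence association (p = D): the second term remains, −3.4 or +3.4 points in the two unequal cases.

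**3. Between-arm difference in Not Adherent.** p − A = −5, −15 or −25 points, against +10 in the Adherent stratum.

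**4. Precision of the doxycycline contrast.** The 95% half-width is approximately 1.96 × √[D(1 − D)/n₁ + p(1 − p)/n₀], with n₁ adherent and n₀ non-adherent men. At 10% non-adherence (n₁ = 110.7, n₀ = 12.3) it is 23 to 28 points. Over 5% to 20% it is 16 to 39 points.

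**5. Example with whole numbers.**

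| Comparison | Counts | Difference (points) | Newcombe 95% CI |
|---|---|---|---|
| Doxycycline: adherent − not | 105/111 vs 8/12 | 27.9 | 7.5 to 55.7 |
| Azithromycin: adherent − not | 94/111 vs 10/12 | 1.4 | −13.0 to 30.0 |
| All Subjects: adherent − not | 199/222 vs 18/24 | 14.6 | 0.8 to 34.8 |
| Not Adherent: doxycycline − azithromycin | 8/12 vs 10/12 | −16.7 | −46.8 to 17.6 |

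Only the last of these four differences is planned.

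**6. Table 30.** PP membership requires the primary adherence definition, so that definition's Not Adherent stratum has no members and its Adherent rows reproduce the cure figures of Table 15. The exception is a subject whom the blinded case review committee (SAP 6.3.2.4) places in PP regardless. The alternative-definition strata need not be empty: a man with 10 or 11 capsules can meet the primary definition and fail the alternative one.

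**The case against.** A reader might infer that the SAP counts placebo capsules as exposure to active drug. It does not: Section 3.3.4 writes the placebo alternative beside each drug, and one arm-blind rule is a natural choice in a double-dummy trial. Nothing here argues against using that rule to define PP.

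A reader might also infer that the planned tables cannot show an adherence association at all. That too goes beyond the documents. The doxycycline rows in Tables 28 and 29 give n, N, the cure proportion and a Wilson interval in each stratum, undiluted. Only the subtraction and its interval are missing.

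Three further points have weight:

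- The SAP plans no contrast between strata for any subgroup, and the layout matches its exploratory outcome measure. The All Subjects row is house format, and the pooled contrasts above arise only if a reader subtracts one such row from another. This is fair, but the objective asks for an effect of adherence, and only for adherence does the subgroup label mean different things in the two arms.
- If capsule-taking is similar in both arms, the Not Adherent difference asks a legitimate question: how the two regimens compare in men who do not finish their capsules. That stands, and it is why a footnote is enough. It is not an adherence effect. The similarity is also not assured, since the protocol records drug intolerance as a reason for missed doses.
- A contrast in the ITT table could mislead. SAP 6.5 imputes unknown cure as failure, while take-home adherence is learned at the follow-up interview. Men lost early may have neither, and classing them Not Adherent would build in an association. The remedy has to avoid this.

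**Conclusion.** The concern holds in a limited form. The capsule-count rule measures active-drug adherence in the doxycycline arm. In the azithromycin arm it does so only through the observed first dose. No planned estimate with an interval addresses the exploratory objective, and the pooled rows dilute any doxycycline association: by half under equal non-adherence, and to about 30% to 70% of its size at 20% versus 5%. These sizes rest on the assumed non-adherence and non-adherent cure rates, and on azithromycin cure not depending on the placebo count. The structural points do not depend on the assumed rates.

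Severity is minor. SAP 6.4 disclaims definitive subgroup conclusions, and the primary complete-case (CC) analysis does not use adherence. A reader might take a negative difference in the Not Adherent stratum as evidence that azithromycin works better. The plan makes no such claim, and with about 12 men per arm the interval would usually be too wide to suggest it, as in the example.

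**What to change.** 1. **Table 28 (CC):** add the adherent minus not-adherent difference in cure within the doxycycline arm, with a Newcombe 95% interval (the method already in SAP 6.1.1), labelled a non-randomised, exploratory association.
2. **Azithromycin rows:** label the corresponding contrast placebo-capsule adherence, to be read as a behavioural control.
3. **All Subjects rows:** drop or footnote them. Footnote also that the between-arm difference within a stratum is not an adherence effect.
4. **Table 29 (ITT):** show subjects with unknown adherence as a separate category, and present no adherence contrast that depends on outcomes imputed as failure. The Listing 11 shell allows only compliant or non-compliant, so it needs the same third value.
5. **Table 30 (PP):** keep only the alternative-definition strata.
6. **Implementation note:** correct the table numbers while editing it.

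No new data are needed: NAAT results are in Listing 6 and dosing, vomiting, re-treatment and capsule counts are in Listing 11. The cost is SAP wording and table-shell edits. The downside is a small non-adherent stratum and a wide interval, a limit the planned tables already have.
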